2.3.3 Pharmacokinetics population

The PK population will be defined as all patients who received at least 1 dose of GZ/SAR402671 and who have at least one PK assessment.

Part 1: Dose escalation phase

Pharmacokinetics data in Part 1 will be described separately for non-Japanese and Japanese patients:

- The Part 1 non-Japanese PK populations will be defined as all non-Japanese patients randomized in Part 1 who received at least 1 dose of GZ/SAR402671 and who have at least one PK assessment
- The Part 1 Japanese PK populations will be defined as all Japanese patients randomized in Part 1 who received at least 1 dose of GZ/SAR402671 and who have at least one PK assessment

Part 2: Treatment phase

The Part 2 PK population will be defined as all patients randomized in Part 2 who received at least 1 dose of GZ/SAR402671 and who have at least one PK assessment.

Patients from Part 1 who are rerandomized in Part 2 will not be included in Part 2 PK population, and will be described separately.

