2.3.4 Pharmacodynamic population

The pharmacodynamic population will be defined as all patients who received at least 1 dose of the double-blind IMP and who have at least one pharmacodynamics assessment.

Part 1: Dose escalation phase

Pharmacodynamics data in Part 1 will be described separately for non-Japanese and Japanese patients:

- The Part 1 non-Japanese pharmacodynamics populations will be defined as all non-Japanese patients randomized in Part 1 who received at least 1 dose of double-blind IMP and who have at least one pharmacodynamics assessment
- The Part 1 Japanese pharmacodynamics populations will be defined as all Japanese patients in Part 1 who received at least 1 dose of double-blind IMP and who have at least one pharmacodynamics assessment

Part 2: Treatment phase

The Part 2 pharmacodynamics populations will be defined as all patients randomized in Part 2 who received at least 1 dose of GZ/SAR402671 and who have at least one pharmacodynamics assessment.

Patients from Part 1 who are rerandomized in Part 2 will not be included in Part 2 pharmacodynamics population, and will be described separately.

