2.4.6.1 Analyses of pharmacodynamic variables

Pharmacodynamic data will be described separately for Part 1 and Part 2 of the study, and separately for Japanese and non-Japanese patients. Data of patients from Part 1 who are rerandomized in Part 2 will not be included in Part 2 and will be presented separately.

Part 1: Dose escalation phase

For all pharmacodynamics parameters, raw data and percent change from baseline will be summarized in descriptive statistics by treatment group and scheduled time of measurement for each population separately (Japanese and non-Japanese patients). No formal statistical comparison will be made.

Additionally, graphs over time will be presented plotting mean +/- SD by treatment group for each population separately (Japanese and non-Japanese patients).

Part 2: Treatment phase

In Part 2, pharmacodynamics data will be presented separately for the two following periods:

- Analysis of the 52-week blinded treatment period of Part 2. This analysis will present pharmacodynamics data from baseline to 52 weeks. Pharmacodynamic analyses will compare the two treatment arms:
 - Placebo
 - GZ/SAR402671 15mg
- Analysis of the 156-week treatment period. This analysis will present all pharmacodynamics data from baseline to 156 weeks, combining the 52-week blinded treatment period and the 104-week long-term follow-up period. Pharmacodynamic analyses will compare the two treatment strategies:
 - Delayed start: patients randomized to receive placebo for 52 weeks, then GZ/SAR402671 15mg for 104 weeks.
 - Early start: patients randomized to receive GZ/SAR402671 15mg for 52 weeks, then continued GZ/SAR402671 15mg for 104 weeks.

Percent change from baseline to Week 26 and Week 52 in plasma GL-1 will be analyzed using a MMRM including data available at Week 2, Week 4, Week 13, Week 26, Week 39 and Week 52 analysis time windows (as defined in Table 6). The model will include the fixed categorical effects of treatment group (GZ/SAR402671 versus placebo), randomization strata (use of levodopa/PD medication: yes/no, MoCA score <26: yes/no and severe GBA mutation: yes/no), time point (as defined in Table 6), treatment-by-time point interaction, randomization strata-by-time point interaction as well as the continuous fixed covariates of baseline and the baseline-by-time point interaction

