Percent change from baseline to Week 52 in CSF GL-1 will be analyzed using an Analysis of Covariance (ANCOVA). The model will include the fixed categorical effects of treatment group (GZ/SAR402671 versus placebo), randomization strata (use of levodopa/PD medication: yes/no, MoCA score <26: yes/no and severe GBA mutation: yes/no), as well as the continuous fixed covariate of baseline.

For all other continuous exploratory endpoints, descriptive statistics by visit will be provided for each treatment arm. Summary statistics (including number of available data, mean, SD, median, minimum and maximum) will be presented for value, change from baseline and percent change

from baseline (when applicable). Further analyses using MMRM (if repeated assessments) or ANCOVA (if single assessment) may be performed when appropriate.

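### The Part 2 pharmacodynamic population requires a dose of active drug, which removes the placebo arm from the planned GL-1 comparison or keeps only its roll-over patients

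*SAP*

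**What the plan says.** Section 2.3.4 opens with a general rule: "The pharmacodynamic population will be defined as all patients who received at least 1 dose of the double-blind IMP", plus at least one pharmacodynamic assessment. The Part 1 definitions follow it. For non-Japanese patients the population is "all non-Japanese patients randomized in Part 1 who received at least 1 dose of double-blind IMP and who have at least one pharmacodynamics assessment", and the Japanese definition uses the same dosing condition.

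The Part 2 definition changes the condition: "The Part 2 pharmacodynamics populations will be defined as all patients randomized in Part 2 who received at least 1 dose of GZ/SAR402671", again with at least one pharmacodynamic assessment. The next sentence excludes Part 1 patients who were re-randomized.

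Section 2.4.6 says that pharmacodynamic variables are presented for the Section 2.3.4 population. For the 52-week blinded period, Section 2.4.6.1 names two arms to compare, placebo and GZ/SAR402671 15 mg, and specifies two models:

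- Plasma GL-1: an MMRM of percent change to Week 26 and Week 52.
- CSF GL-1: "Percent change from baseline to Week 52 in CSF GL-1 will be analyzed using an Analysis of Covariance (ANCOVA").

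For each model the text reads: "The model will include the fixed categorical effects of treatment group (GZ/SAR402671 versus placebo").

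**The concern.** A pharmacodynamic comparison with placebo needs placebo patients in its analysis population. The Part 2 condition is the one used for pharmacokinetics in Section 2.3.3: "The Part 2 PK population will be defined as all patients randomized in Part 2 who received at least 1 dose of GZ/SAR402671". It suits that purpose because placebo patients have no drug concentration to measure. In Section 2.3.4 it removes the comparator. A carry-over from the PK section is the likely cause, but that is inference.

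Section 1.2.2.2 makes GL-1 response in plasma and CSF over 52 weeks a Part 2 secondary objective, and the MMRM and ANCOVA are the models the SAP names for it. Section 1 says that the methods are fixed before unblinding. With two incompatible definitions and no rule for which prevails, the choice could be made after unblinding, and that protection would be lost for this objective.

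**Working it through.** **Definitions side by side (Section 2.3.4)**

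| Definition | Dose required | Placebo patient qualifies? |
|---|---|---|
| General | double-blind IMP | yes |
| Part 1, non-Japanese and Japanese | double-blind IMP | yes |
| Part 2 | GZ/SAR402671 | only if later given active drug |

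**When a placebo patient can receive GZ/SAR402671.** Sections 2.4.3.1, 2.4.4 and 2.4.6.1 all place this in the 104-week long-term follow-up, after 52 weeks on placebo. Section 2.4.3.1 counts such exposure only for placebo patients who actually received the drug, so it does not assume that all do.

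**Two readings of the Part 2 rule**

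1. *The dose must fall in the blinded period.* No placebo patient dosed as randomized qualifies. The treatment term has a single level and the contrast cannot be estimated.
2. *Any Part 2 dose counts.* A placebo patient qualifies only through a dose taken after Week 52. A GZ/SAR402671 patient qualifies from the first dose, given one pharmacodynamic assessment, including a patient who stops early.

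The second reading affects the analyses as follows:

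- **Plasma MMRM (Weeks 2 to 52).** GZ/SAR402671 patients who stop early still contribute their early visits. Placebo patients who stop early and never take active drug are dropped entirely.
- **CSF ANCOVA (Week 52).** A patient without a Week 52 CSF value contributes in neither arm, so the imbalance is smaller. Placebo patients with a Week 52 sample who do not go on to active drug are still lost, while their GZ/SAR402671 counterparts stay.
- **First-step analysis.** Section 4 sets the cut-off at the last patient's Week 52 visit. A placebo patient who reaches Week 52 close to that date may not yet have had active drug, so inclusion could depend on enrolment date.
- **156-week analysis.** The delayed-start group is restricted to patients who rolled over, and the early-start group is not.

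**Planned arm size (Section 1.3.2).** Inputs: difference 4.06, SD 10.01, two-sided alpha 0.05, power 80%, loss about 10%.

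- Normal approximation: n = 2 × (1.960 + 0.842)² × (10.01 / 4.06)² = 2 × 7.849 × 6.079 = 95.4, so 96 per arm; 96 / 0.90 = 106.7, so 107.
- t-test: 97 per arm gives 80.2% power; 97 / 0.90 = 107.8, so 108.

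The SAP's 108 per arm reproduces. It was set for MDS-UPDRS and serves here only as the planned size of the placebo arm.

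**Placebo patients left under the literal rule:** 108 × r, where r is the share who later take GZ/SAR402671. The SAP does not give r, so these values are assumptions.

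| r | Placebo patients kept |
|---|---|
| 0 | 0 |
| 0.25 | 27 |
| 0.50 | 54 |
| 0.75 | 81 |
| 0.90 | 97 |
| 1.00 | 108 |

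The 0.90 row borrows the 10% allowance for early termination or unevaluable patients, which is not a roll-over rate. It illustrates and does not bound. Under the double-blind IMP rule the comparison is up to 108 versus 108, or about 97 versus 97 after 10% loss (108 × 0.90 = 97.2).

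**The case against.** The strongest reply has four parts.

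- **Another route exists.** Section 2.1.3.3 lists GL-1 changes among the exploratory efficacy endpoints, and Section 2.3.1 makes the Part 2 ITT population primary for all efficacy endpoints. All randomized placebo patients would then appear in a GL-1 summary. This is true, but Section 2.4.4.3 commits only to descriptive summaries by arm for these endpoints and leaves further MMRM or ANCOVA optional. It does not repair the models that Section 2.4.6.1 specifies on the pharmacodynamic population.
- **The endpoints are not confirmatory.** GL-1 is absent from the secondary endpoints in Section 2.1.3.2 and from the hierarchy in Section 2.4.4.4. This stands. No type I error claim, sample size or primary result depends on the flag.
- **The intent is plain.** The general definition, the Part 1 definitions and the named placebo arm all point to double-blind IMP. That is probably so, but it also confirms that the Part 2 sentence is wrong. That sentence is the more specific one, and a programmer would normally apply it. An empty arm would show at the first model run; a roll-over-only arm would fit and look plausible.
- **The size is unknown.** This also stands. Follow-up entry rules are left to the protocol, r is not given, and the selection effect cannot be quantified from the SAP.

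**Conclusion.** The concern holds. The Part 2 definition contradicts the rest of Section 2.3.4 and the placebo contrasts in Section 2.4.6.1. Applied as written, it leaves no placebo arm or one selected on roll-over after Week 52, with anywhere from 0 to 108 of the 108 planned patients depending on an unstated share. The active arm carries no matching restriction beyond one dose and one assessment.

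This rests on the SAP's own account that placebo patients receive GZ/SAR402671 only in long-term follow-up. The damage is confined to the pharmacodynamic analyses: plasma and CSF GL-1, which serve a stated secondary objective, and the other biomarkers presented on this population. The primary and secondary clinical endpoints use the Part 2 ITT population and are unaffected. Because the error removes or distorts the comparator in a prespecified comparison, it should be corrected before unblinding.

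**What to change.** In the Part 2 definition of Section 2.3.4, replace the requirement for a dose of GZ/SAR402671 with at least one dose of the double-blind IMP in Part 2. Keep the requirement for at least one pharmacodynamic assessment and the exclusion of re-randomized Part 1 patients. While the sentence is open, state whether patients are analyzed as randomized or as treated. The PK population in Section 2.3.3 needs no change.

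The cost is one phrase in the SAP and one population flag in the programs. No extra data or patients are needed, and no sample size or power figure changes.

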2.4 STATISTICAL METHODS

2.4.1 Demographics and baseline characteristics

Demographic and baseline characteristics will be presented for the randomized population, separately for Part 1 and Part 2 of the study. In Part 1, data will be presented separately for Japanese and non-Japanese patients.

Continuous data will be summarized using the number of available data, mean, standard deviation (SD), median, minimum and maximum for each treatment arm. Categorical and ordinal data will be summarized using the number and percentage of patients in each treatment arm.

Parameters will be summarized on the randomized population analyzed in the treatment group to which they were randomized.

Parameters described in [Section 2.1.1](#) will be summarized by treatment group and overall treatment groups using descriptive statistics.

Medical/surgical history will be summarized in each treatment arm by primary SOC, HLT and PT. Events will be sorted by SOC internationally agreed order and decreasing frequency of PT based on the incidence in the overall treatment arm.

P-values on demographic and baseline characteristic data will not be calculated.

2.4.2 Prior or concomitant medications

Prior and concomitant medications will be presented for the randomized population, separately for Part 1 and Part 2 of the study. In Part 1, data will be presented separately for Japanese and non-Japanese patients.

PD medications will include:

- Dopamine replacement therapies (eg: levodopa/carbidopa)
- Dopamine agonists (eg: pramipexole, ropinerole, bromocriptine)
- Monoamine oxidase B inhibitors (eg: rasagiline)
- Catechol-O-methyltransferase inhibitors (eg: entacapone, tolcapone)
- Anticholinergics (eg: artane, cogentin)

A list of ATC codes to be used in determining PD medications will be provided by the Coding Department.

These medications will be summarized by treatment group, by chemical class and standardized medication name.

Other medications will be summarized by treatment group according to the WHO-DD dictionary, considering the first digit of the anatomic category (ATC) class (anatomic category) and the first 3 digits of the ATC class (therapeutic category). All ATC codes corresponding to a medication will be summarized, and patients will be counted once in each ATC category (anatomic or therapeutic) linked to the medication. Therefore patients may be counted several times for the same medication.

The tables for prior PD medications and prior other medications will be sorted by decreasing frequency of ATC followed by all other therapeutic classes based on the overall incidence across treatment groups. In case of equal frequency regarding ATCs (anatomic or therapeutic categories), alphabetical order will be used.

The tables for concomitant and post-treatment medications (for PD medications and other medications) will be sorted by decreasing frequency of ATC followed by all other therapeutic classes based on the incidence in the GZ/SAR402671 group (pool of all doses for Part 1). In case of equal frequency regarding ATCs (anatomic or therapeutic categories), alphabetical order will be used.

2.4.3 Extent of investigational medicinal product exposure and compliance

The extent of IMP exposure and compliance will be assessed and summarized by actual treatment within the safety population ([Section 2.3.2](#)), separately for Part 1 and Part 2 of the study. In Part 1, data will be presented separately for Japanese and non-Japanese patients.

2.4.3.1 Extent of investigational medicinal product exposure

The extent of IMP exposure will be assessed by the duration of IMP exposure.

Within each part of the study, duration of IMP exposure is defined as last dose date – first dose date + 1 day, regardless of unplanned intermittent discontinuations (see [Section 2.5.3](#) for calculation in case of missing or incomplete data).

In Part 2, the duration of exposure to GZ/SAR402671 will be calculated for both patients randomized to the GZ/SAR402671 arm and patients randomized to the placebo arm who received GZ/SAR402671 during the 104-week long term follow-up period.

The duration of exposure to GZ/SAR402671 and the duration of exposure to placebo will be summarized descriptively within each treatment arm, as a quantitative variables (number, mean, SD, median, minimum, and maximum). In addition, duration of treatment exposure will also be summarized cumulatively by numbers and percentages for each of the following categories:

- Part 1:
 - ≥ 1 day
 - ≥ 4 weeks
 - ≥ 8 weeks
 - ≥ 12 weeks
 - ≥ 24 weeks
 - ≥ 36 weeks
- Part 2:
 - ≥ 1 day
 - ≥ 4 weeks
 - ≥ 8 weeks
 - ≥ 13 weeks
 - ≥ 26 weeks
 - ≥ 39 weeks
 - ≥ 52 weeks
 - ≥ 78 weeks
 - ≥ 104 weeks
 - ≥ 130 weeks

- ≥ 156 weeks

In addition, the cumulative exposure to treatment (number of patient-years of exposure) will be summarized.

2.4.3.2 Compliance

A given administration will be considered noncompliant if the patient did not take the planned dose of treatment as required by the protocol. No imputation will be made for patients with missing or incomplete data.

Treatment compliance will be defined as the ratio: actual number of capsules taken / (intended daily number of capsules * duration of treatment exposure) * 100, where the intended daily number of capsules equals to:

- Part 1:
 - 1 capsule per day for patients in Cohort 1 (4mg or placebo)
 - 2 capsules per day for patients in Cohort 2 (8mg or placebo)
 - 1 capsule per day for patients in Cohort 3 (15mg or placebo)
- Part 2:
 - Double blind treatment period: 1 capsule once per day (15mg or placebo) for 52 weeks
 - Long term follow-up period: 1 capsule once per day (15mg) for additional 104 weeks

Treatment compliance will be summarized descriptively (N, mean, SD, median, min, and max). The percentage of patients with compliance $< 80\%$ will be summarized.

Cases of overdose are reported in the AE e-CRF pages as AESI if symptomatic or AE if asymptomatic. The reported cases of overdose will be described in the AE analysis (see [Section 2.1.4](#)).

2.4.4 Analyses of efficacy endpoints

Efficacy endpoints will be presented for the efficacy populations (see [Section 2.3.1](#)), separately for Part 1 and Part 2 of the study. In Part 1, data will be presented separately for Japanese and non-Japanese patients.

In Part 2, efficacy data will be presented separately for the two following periods:

- Analysis of the 52-week blinded treatment period of Part 2. This analysis will present efficacy data from baseline to 52 weeks. Efficacy analyses will compare the two treatment arms:
 - Placebo
 - GZ/SAR402671 15mg

- Analysis of the 156-week treatment period. This analysis will present all efficacy data from baseline to 156 weeks, combining the 52-week blinded treatment period and the 104-week long-term follow-up period. Efficacy analyses will compare the two treatment strategies:
 - Delayed start: patients randomized to receive placebo for 52 weeks, then GZ/SAR402671 15mg for 104 weeks.
 - Early start: patients randomized to receive GZ/SAR402671 15mg for 52 weeks, then continued GZ/SAR402671 15mg for 104 weeks.

Details of timing of these two analyses is presented in [Section 4](#).

2.4.4.1 Analysis of primary efficacy endpoint(s)

Part 1: Dose escalation phase

The primary endpoint in Part 1 is safety of each dose cohort. MDS-UPDRS in Part 1 will be analyzed for exploratory purpose (see [Section 2.4.4.3](#)).

Part 2: Treatment phase

All analyses of efficacy endpoints in Part 2 of the study will not include patients from Part 1 who are rerandomized in Part 2. Efficacy data in patients from Part 1 will be described separately, with no formal statistical testing.

Estimand

The primary estimand is the difference in mean change from baseline to Week 52 in MDS-UPDRS Part II+III score if all randomized patients had completed the treatment period, regardless of whether or not patients required initiation or intensification of levodopa/PD therapy.

A secondary estimand will be the difference in mean change from baseline to Week 52 in MDS-UPDRS Part II+III score, regardless of whether or not patients completed the treatment period or required initiation or intensification of levodopa/PD therapy.

Statistical hypotheses

Let μ_0 and μ_1 be the population means of the change from baseline to Week 52 in MDS-UPDRS Part II+III score under placebo and GZ/SAR402671, respectively. The primary hypothesis that will be tested is “H0: $\mu_0 = \mu_1$ ” versus “H1: $\mu_0 \neq \mu_1$ ”.

Primary analysis

In accordance with the primary estimand, the primary analysis will exclude data collected after premature treatment discontinuation. For patients who prematurely discontinued study treatment, any MDS-UPDRS assessed after the date of last administration of the IMP + 7 days

(corresponding to approximately 5 half-lives of GZ/SAR402671) will be excluded from the primary analysis.

Change from baseline in MDS-UPDRS Part II+III score will be analyzed using a mixed effect model with repeated measures (MMRM). All data available at Week 13, Week 26, Week 39 and Week 52 analysis time windows (as defined in Table 6) will be used in the primary analysis. For patients who prematurely discontinued study treatment, data assessed more than 7 days after the date of last administration of the IMP will be excluded from the primary analysis.

The model will include the fixed categorical effects of treatment group (GZ/SAR402671 versus placebo), randomization strata (use of levodopa/PD medication: yes/no, MoCA score <26: yes/no and severe GBA mutation: yes/no), time point (as defined in Table 6), treatment-by-time point interaction, randomization strata-by-time point interaction as well as the continuous fixed covariates of baseline MDS-UPDRS Part II+III score and the baseline-by-time point interaction.

This model will be run using SAS Mixed procedure with an unstructured correlation matrix to model the within-patient errors. Parameters will be estimated using restricted maximum likelihood method. Denominator degrees of freedom will be estimated using Kenward-Roger approximation. This model will provide baseline adjusted least-squares means estimates at Week 52 for both treatment groups with their corresponding standard errors (SEs) and 95% confidence intervals (CI). The difference in baseline adjusted least-squares means will be used to compare the GZ/SAR402671 group to the placebo group, at the 2-sided 0.05 level.

Within group least-squares means and standard errors will be calculated using weights equal to the observed proportion of patients in strata variable levels in the study population (i.e. “population weight”) rather than equal weights. Population weights are considered more appropriate than equal coefficients due to expected unbalances in the study population between levels of the randomization stratification factors.

In addition, the relative reduction versus placebo will be calculated as:

$$\text{Relative reduction (\%)} = \left(1 - \frac{\text{LS mean change at Week 52 in GZ/SAR402671 arm}}{\text{LS mean change at Week 52 in placebo arm}} \right) \times 100$$

Relative reduction will be presented with 95% confidence interval using Fieller method. This confidence interval will be calculated provided a significant change is observed in the placebo arm at the 0.05 level. In addition, the posterior probability that GZ/SAR402671 achieves a relative reduction by at least 25% and 50% will be calculated using samples from the asymptotic distribution of LS means from the two treatment arms.

Sensitivity analysis including data collected after treatment discontinuation

A sensitivity analysis will estimate the difference in mean change from baseline to Week 52 in MDS-UPDRS Part II+III score regardless of whether or not patients completed the treatment period. In this sensitivity analysis, MDS-UPDRS assessed more than 7 days after the last IMP

administration will be included in the analysis. The MMRM model described as primary analysis will be repeated after inclusion of these data.

Sensitivity analysis with slope-based analysis

The rate of change in MDS-UPDRS Part II+III score from baseline to Week 52 will be estimated using a slope-based analysis assuming linear change from baseline to Week 52. A linear mixed effect model will be fitted, which will include the fixed effect of treatment group (GZ/SAR402671 versus placebo), randomization strata (use of levodopa/PD medication: yes/no, MoCA score <26: yes/no and severe GBA mutation: yes/no), time in years from baseline (as continuous variable), treatment*time interaction and randomization strata*time interaction, and will include random intercept and slope. Time (in years) will be calculated as (date of assessment – date of randomization + 1) / 365.25.

Within group mean slope will be obtained from the linear mixed effect and difference in slopes will be presented with the 95% confidence intervals. P-value of the comparison of slopes will be presented for descriptive purpose only.

Relative reduction in slope will be presented with 95% confidence interval. The posterior probability that GZ/SAR402671 achieves a relative reduction in slope by at least 0%, 25% and 50% will be calculated.

[figure not shown]
Sensitivity analysis exploring alternative approach regarding missing data

The MMRM model relies on the “missing-at-random” (MAR) assumption. As the possibility for a not-missing-at-random (NMAR) missingness mechanism cannot be excluded, a sensitivity analysis to explore the impact of nonignorable missingness on the primary efficacy analysis will be conducted.

The sensitivity analysis will be based on a pattern-mixture model. Multiple imputations will be generated using a “Copy Increment from Reference” (2) method. Assumptions underlying this method are the following:

- For patients in the GZ/SAR402671 arm who prematurely discontinued the IMP before 52 weeks and had missing data, it will be assumed that after treatment discontinuation, changes in mean profile of the primary endpoint will follow that of the placebo arm, starting from the last observed value. This assumption is considered reasonable in a progressive disease such as PD, where treatment is expected to slow down the progression, but after stopping therapy the disease would continue to progress (3). A schematic representation of the imputation model is provided in [Figure 3](#).
- Missing data in patients from the placebo arm or in patients from the GZ/SAR402671 arm who completed the 52-week treatment period will be imputed assuming they are MAR

Figure 3 - Schematic representation of imputation of missing data – Sensitivity analysis using Copy Increment from Reference (CIR) method

Multiple imputations will be generated using SAS macros developed by James Roger (4). The imputation model will include adjustment for randomization strata (use of levodopa/PD medication: yes/no, MoCA score <26: yes/no and severe GBA mutation: yes/no).

Missing values will be imputed 1,000 times to generate 1,000 complete data sets. Each completed dataset will be analyzed using an analysis of covariance (ANCOVA) of change from baseline to Week 52 in MDS-UPDRS Part II+III score, including the fixed categorical effects of treatment group (GZ/SAR402671 versus placebo), randomization strata (use of levodopa/PD medication: yes/no, MoCA score <26: yes/no and severe GBA mutation: yes/no), as well as the continuous fixed covariates of baseline value. The final results will be obtained by combining the least squares means and least squares mean differences from these 1,000 analyses, using Rubin’s formula.

Sensitivity analysis exploring alternative approach regarding assessment during the OFF state

In the protocol, instructions were given to assess MDS-UPDRS during the OFF state. Patients should not take their PD medications for at least 12 hours prior to the assessment. Different sensitivity analyses will explore the impact of assessment of MDS-UPDRS performed less than 12 hours after intake of PD medication.

These sensitivity analyses will be performed as following:

- Excluding any MDS-UPDRS assessed less than 12 hours after intake of PD medication (irrespective of clinical state)
- Excluding any MDS-UPDRS assessed less than 6 hours after intake of PD medication (irrespective of clinical state)
- Excluding any MDS-UPDRS assessed less than 12 hours after intake of PD medication and for which the clinical state was recorded as “ON”.
- Excluding any MDS-UPDRS assessed less than 6 hours after intake of PD medication and for which the clinical state was recorded as “ON”.

The MMRM model described as primary analysis will be repeated after exclusion of these data.

Sensitivity analyses assessing randomization strata

A sensitivity analysis will estimate the difference in mean change from baseline to Week 52 in MDS-UPDRS Part II+III score after including the actual strata derived from data instead of the strata recorded in IVRS (use of levodopa/PD medication: yes/no, MoCA score <26: yes/no and severe GBA mutation: yes/no). The purpose of this analysis will be to assess the impact of discrepancies observed between the strata recorded in the IVRS and the ones derived from data. The MMRM model described as primary analysis will be repeated after including the actual strata.

Secondary analysis

A secondary analysis will describe the number and percentage of patients with MDS-UPDRS Part II+III score improvement, no change or worsening at Week 52 based on minimal clinically important difference threshold values in patients with Hoehn&Yahr 1&2 (5):

- Improvement will be defined as change in MDS-UPDRS Part II+III ≤ -4.3
- Worsening will be defined as change in MDS-UPDRS Part II+III ≥ 3.9
- No change will be defined as change in MDS-UPDRS Part II+III > -4.3 and < 3.9

Patients without any available assessment at Week 52 will be considered as worsened.

Subgroup analyses

The MMRM model described as primary analysis will be repeated in each of the following subgroups as appropriate, the p-values will not be adjusted for multiplicity and will be provided for descriptive purpose only, and forest plots will be provided:

- Sex (Male vs. Female);
- Age (≤ 60 vs. > 60);
- GBA mutations (severe vs. non severe) : Severe GBA mutation subgroup will be defined using actual subgroup (not randomization stratum as per IVRS);

- Prior PD medications (yes vs. no): Prior PD medication subgroup will be defined using actual subgroup (not randomization stratum as per IVRS);
- Time since onset of symptoms (≤ 6 years vs > 6 years);
- Time since diagnosis (≤ 6 years vs > 6 years);
- MDS-UPDRS Part II+III at baseline (≤ 35 vs. > 35);
- Hoehn and Yahr at baseline (< 2 vs. ≥ 2);
- MoCA score at baseline (< 26 vs. ≥ 26): MoCA score subgroup will be defined using actual subgroup (not randomization stratum as per IVRS);

Unless otherwise specified (see below), for each subgroup analysis, the MMRM model will include the fixed categorical effects of treatment group, randomization strata as per IVRS, subgroup factor, time point, treatment-by-time point interaction, strata-by-time point interaction, subgroup factor-by-time point interaction, treatment-by-subgroup factor interaction, and treatment-by-subgroup-by-time point interaction, as well as the continuous fixed covariates of baseline value and baseline value-by-time point interaction. Exceptions will be made for the following subgroup analyses:

- For subgroup analyses by GBA mutation, the MMRM will not include the randomization stratum of severe GBA mutation (yes/no)
- For subgroup analyses by prior PD medication, the MMRM will not include the randomization stratum of use of levodopa/PD medication (yes/no)
- For subgroup analysis by MoCA score at baseline, the MMRM will not include the randomization stratum of MoCA score < 26 (yes/no)
- For subgroup analysis by MDS-UPDRS Part II+III at baseline (≤ 35 vs. > 35), the MMRM will not include adjustment for baseline

